6. COGNITIVE DEVELOPMENT ASSESSMENT

The Developmental Milestones Checklist (DMC-III) will be used to evaluate the development of motor and language skills in 240 children at baseline in this study. The DMC-III includes three subscales: gross motor, fine motor, and language. The original version of the DMC-III was designed for children aged 3 to 24 months. The updated DMC-III includes additional items to assess children aged 2 to 8 years. The DMC-III requires parent interview for all items and includes optional direct observation of the child for all items. For this study, data collectors will include both parent interview and direct observation for all items where possible.

Materials for observation items:

- Pens
- White paper
- A ball (child-size football/soccer ball)
- A small toy
- Small grains in a box
- A pull-toy
- A color sheet printed with boxes of the following colors : blue, green, yellow, brown, purple, white, grey, orange, red, black, and pink

- 5 coins

Preparing the assessment session for observation items:

2.1 Before the assessment session

- Check** that you have all of the **equipment** and record **forms** required using the checklist.

2.2 When you arrive at the child's house

- Greet** the mother or caregiver accompanying the child.
- Introduce** yourself and outline the purpose of the visit
- Approach** the child for the first time in the presence of the mother / caregiver
- Observe** carefully the child's reaction to yourself and the situation as it unfolds.
- Confirm** that the child is in good **health**. **DO NOT ASSESS A CHILD WHO IS UNWELL**. If the child is sick, conduct the interview portion of the visit and make an appointment to return at a later date to conduct the observation items.

2.3 Guidelines for the testing location

- The testing location should be a place where there is shade, flat ground, maximum privacy, and space for movement.
- Take time to select the largest, quietest location that allows you to run around. You can sit in one place and run around elsewhere.
- Remove** possible **distractors** before starting to assess.
- If possible, position the child **facing a wall** to minimize distractions.
- Make sure the child and mother are settled and **comfortable**.
- Take good care to ensure the safety of the children. Look out for potential hazards.
- If others gather to watch, ask them politely to leave. Explain that the child might be shy if he or she is being watched by others. If necessary, ask for the mother's help to disperse the crowd.

2.4 Setting up the equipment.

- Arrange** equipment where it will be easily accessible to you.
- Explain** to the family member who accompanies the child their role. To
 - provide comfort to their child by their presence
 - encourage the child to participate
 - (if necessary) to help communicate the instructions to the child. Help them to understand the game, but NOT to assist the child to complete tasks.

2.5 Settling the child

- Use** the name the child is called by throughout the session. Whenever you need

to get the child's attention to ask a question or give an instruction, say his or her name.

- b) **Re -introduce** yourself to the child
- c) **Invite** the child to participate in an activity.
- d) **Engage** the child with some of the equipment/activities. This may include a warm up activities, separate from the main assessment.
- e) In general, children respond well when we smile, are enthusiastic, playful, and affectionate.

2.6 General instructions for administering fine and gross motor items:

- a) **First**, demonstrate the task.
- b) **Second**, help the child to do the task. Give support where necessary until you are certain that the child can complete the task unsupported. Remove any support provided in stages.
- c) **Third**, tell the child to do the task alone, without assistance.

2.7 During assessment.

- a. Carry out all activities on flat and even ground.
- b. Child should be in a clear space away from furniture / walls.
- c. The inclusion of mother and siblings in these activities often aids and encourages the target child to feel less inhibited.
- d. **Give** precise and clear instructions to the child, following manual guidelines.
- e. **Move** from one task to the other in a systematic way.
- f. **Pay attention** to the child at all times.
- g. **Praise** the child for effort, NOT success in an item.
- h. **Return** assessment material to the box on completion of the item. Take out the material for one item at a time and replace it when you have finished. Sometimes you may take out the material for the next item before replacing the material for the previous item, if this is necessary to keep the child's attention. However, in this case, replace the material for the previous item immediately after engaging the child's attention with the new item.
- i. **Take a break** if the child gets tired or becomes distressed. In general, it is a good idea to take a break at least every 30 minutes.
- j. **If necessary, remind** the accompanying family member of their role in the assessment.

Do NOT:

- 1) **Crowd** the assessment area with used items, this will distract the child.
- 2) **Hurry** the child.

2.8 Strategies for handling children who refuse

- a) Have the mother demonstrate the task and encourage the child to do it

- b) Involve other children who are around, perhaps an older sibling. Have the other child do it and see if the child will do the task along with another child.
- c) Give the child a drink and a break, let the child rest or play for a few minutes
- d) Promise to give the child a sweet if he/she does the task

2.9 Ending the assessment

- a) **Formally** end the session by thanking everyone.
- b) **Before you leave the house**
 - i. **Read** through your form carefully.
 - ii. **Confirm** each section/ checklist is filled fully.
- c) Check all equipment is packed properly. (Use checklist to help you.)

2.10 Before the next session

CLEAN AND DISINFECT THE EQUIPMENT EVERY DAY.

Administration procedures

In each subscale, the items are arranged in order from the earlier acquired skill (for example, sits supported) to the later acquired skill (for example, sits alone on the floor). The arrows in the left-hand margin show the start points for the child's age. Start at the item appropriate for the child's age. If the child scores 0, go to the previous start point. If the child scores 1 or 2, continue to the next item. Stop after 4 consecutive scores of 0. Refer to the DMC-III Manual for a detailed description of how to administer each item, including probing questions to use if the interviewee has difficulty understanding the question. The DMC-III flipchart includes pictures, which should be used in conjunction with the questions for the two motor subscales.

7. MICROBIOLOGICAL METHODS

Participant names will not be included in laboratory records and samples will be de identified. Therefore, laboratory personnel will be masked, preventing identification of the individuals infected. Lab results will not be available for weeks, if not months. Thus, all individuals will be treated according to their study arm, whether or not their lab tests reveal evidence of infection.

Preparation of Zymo DNA/RNA Shield™

Manufacturer's Product Description

DNA/RNA Shield™ ensures nucleic acid stability during sample storage/transport at ambient temperatures, preserving the genetic integrity and expression profiles of samples. There is no need for refrigeration or specialized equipment. DNA/RNA Shield™ effectively lyses cells and inactivates nucleases and infectious agents (virus), and it is compatible with various collection and storage devices (vacuum tubes, swabs, nasal, buccal, fecal, etc.).

Materials Required

| Product | Supplier | Catalog No. |
|--|---------------------|--|
| DNA/RNA Shield™ 1X solution | Zymo Research Corp. | R1100-50 (50 ml) R1100-250 (250 ml) |
| 2ml Loop Screw Cap Micro Tube, PCR Performance Tested (DNA-, DNase-, RNase-, & PCR inhibitor-free) | Sarstedt Inc. | 72.694.416 |
| Insert for Loop Screw Cap, Violet | Sarstedt Inc. | 65.713.007 |

Procedure

1. Prepare tubes by adding violet cap inserts to the top of each tube (these are for color coding purposes to help distinguish the DNA/RNA Shield solution from other media being used in the field).
2. Before aliquoting the DNA/RNA Shield, gently mix the solution by either swirling it or inverting the bottle a few times (trying not to create too many bubbles) to ensure that the solution is homogenous. In a clean biosafety cabinet, use sterile technique to aliquot 1 ml of the solution into each 2 ml tube.
3. When you have finished aliquoting, make sure that the cap on each tube has been tightened to prevent tubes from leaking during transport.

Storage and Shelf Life

Store prepared tubes at room temperature (20°C-25°C) until use; do not freeze solution prior to collecting samples. Zymo guarantees the shelf-life of DNA/RNA Shield™ up to 1 year from the date of receipt. Therefore, if the solution is aliquoted right away, then prepared tubes should be good for 1 year. The shelf-life may be longer, depending on storage conditions.

Methods for Resistance Testing

Isolation & Identification of Organisms Using Microbiological Techniques

S. pneumoniae will be isolated from nasopharyngeal swabs using blood and strep select plate, chocolate, and chocolate with bacitracin media. We will identify organisms using gram stain. Standard microbiological handbooks should be referenced for more detailed information.

Laboratory Results Reporting

All lab results will be kept in computer files as well as in hard-copy form by the Microbiologist.

Description of Identification Tests:

We will follow the standard quality control methods already in place at the laboratory. For example, lab staff will perform positive and negative growth controls for all media, and positive controls for all stains and identification tests at a pre-determined schedule.

Catalase Test:

A few drops of 3% hydrogen peroxide are added to colonies removed from agar and smeared onto a clean glass slide, and immediately observed for the release of oxygen or “bubbling.” Bubbling is interpreted as the presence of catalase. Lack of bubbling is a negative test.

Tube Coagulase:

Coagulase plasma is inoculated with an isolated staphylococcal colony and incubated for up to 24 hours at 37°C. Any degree of clot formation is a positive reaction and no clot is a negative reaction.

Latex Agglutination:

A few staphylococcal colonies are mixed with the latex agglutination reagent and observed for agglutination. A positive reaction is agglutination of the latex particles, while no agglutination is a negative reaction.

Optochin Test:

An optochin disc is placed onto a blood agar subcultured plate that has been inoculated with a pure culture of the test organism. Plates are incubated for 24 hours at 35°C in CO₂. If a zone of inhibition of 14 mm or more is formed, then it's *S. pneumoniae*.

Desoxycholate (10%) Test:

A drop of reagent is added to a well-isolated colony on a blood agar plate. Colonies of *S. pneumoniae* will disintegrate after 30 minutes.

Satelliting Growth on Blood Agar:

Colonies resembling Haemophilus are subcultured to a non-selective blood agar plate and cross streaked with Coagulase negative Staphylococcus. Plates are incubated in CO₂ overnight and examined for satellite growth around Staphylococcus.

Microbiological Resistance Testing for Swabs

Resistance testing will be performed using the Kirby Bauer disc diffusion assay or E-test strips (to determine MIC's).

Quality Control

E. coli ATCC 25922, *S. pneumoniae* ATCC 49619, *H. influenzae* ATCC 49247, *S. aureus* ATCC 25923 and 29213 are used for quality control testing of antibiotic discs and E-test strips.

Kirby Bauer Assay

A suspension of the isolate is prepared and turbidity adjusted until it reaches the 0.5 McFarland standard. The suspension is used to inoculate the appropriate susceptibility agar plate for

confluent growth. The plate is allowed to dry. Antimicrobial disks are placed on the agar plates with sterile forceps or tweezers; disks may not be moved once they have touched the plates. After the disks are placed on the plate, the plates are inverted and incubated at 35°C for 16 to 18 hours. After incubation, the diameter of the zones of complete inhibition (including the diameter of the disk) (Figure 2) are measured and recorded in millimeters. The measurements can be made with a ruler or sliding caliper on the undersurface of the plate without opening the lid. The zones of growth inhibition will be compared with the zone-size interpretative table and recorded as susceptible, intermediate, or resistant to each drug tested according to CLSI guidelines (see Appendix).

Figure 2. Results of the disk diffusion assay. This *Shigella* isolate is resistant to trimethoprim-sulfamethoxazole and is growing up to the disk (SXT), the zone of which is recorded as 6 mm.

E-test strips.

In addition, azithromycin Minimum Inhibitory Concentrations (MIC) are determined using E-test strips. A suspension of the isolate is prepared and turbidity adjusted until it reaches the 0.5 McFarland standard. The suspension is used to inoculate the appropriate susceptibility agar plate for confluent growth. The plate is allowed to dry. E-test strips are placed on the agar plates with sterile forceps or tweezers; strips may not be moved once they have touched the plates. After the strips are placed on the plate, the plates are inverted and incubated at 35°C for 20 to 24 hours. The MIC is read where the ellipse intersects the MIC scale on the strip. The MIC will be compared with the interpretative table according to CLSI guidelines (see Appendix).

8. PROTECTION OF HUMAN SUBJECTS

Before the study begins, each site will obtain formal ethical approval from their respective national ethics committee. In addition, local staff will approach community leaders to describe the study and answer any questions. Study staff will proceed only if local leadership consents to participate. For Study One, we will obtain verbal consent from a parent or guardian of all study participants. For Study Two, we will obtain written consent from a parent or guardian for all

study activities, including treatment and examinations. Children will only be included in the study following receipt of consent from the parent or guardian. If, at any time, a parent or guardian elects to withdraw a family member from the study, they will be free to do so. Children with wasting or stunting will be referred for appropriate treatment by trained study personnel to the nearest health center.

Risks and Benefits of Study Procedures

Swabbing Procedures

There are minimal risks to the participant who receives nasopharyngeal, and nares swabbing. Participants may experience some temporary discomfort, but the swabbing involves minimal risk. Any adverse effects, such as nose-bleeds, will be treated immediately by the examiners. Other health care will be provided at no cost to the study participant if necessary to address a study-related adverse health event.

Rectal swabs and stool samples: Rectal swabs are a simple procedure with very minimal risk. Stool sample collection is a non-invasive procedure with no associated risks.

Anthropometric Measurements

There are minimal risks associated with the measuring board, scale, or MUAC tapes aside from anxiety during the measurements. Examiners will do their best to ensure that the parent/guardian of the child understands the process of assessing anthropometric measurements. The examiners will attempt to minimize discomfort for all study participants before, during, and after the measurements are taken. Children with wasting or stunting will be referred for appropriate treatment at the nearest health center.

Antibiotic Resistance and Microbiome in Children Aged 1-59 months in Nouna, Burkina Faso

Manual of Operations and Procedures

NCT number 03187834

Version 1.1 June 2017

Centre de Recherche en Santé de Nouna

University of Heidelberg

Francis I. Proctor Foundation, University of California, San Francisco

Antibiotic resistance and Microbiome in Children Aged 6-59 months in Nouna, Burkina Faso

Statistical Analysis Plan, Version 1.0, June 15 2017

Study Overview

We will randomize 120 households containing 2 or more children aged 6-59 months to one of four study arms: 1) azithromycin, 2) amoxicillin, 3) cotrimoxazole, or 4) placebo. All children will receive 5 days of treatment. Full intervention details can be found in the Manual of Operations and Procedures. Rectal and nasopharyngeal swabs will be collected pre-treatment (baseline) and on Day 9 following the 5 days of treatment. Anthropometric indices (weight, height, and mid-upper arm circumference) will be collected at baseline and Day 35 (one month following treatment completion).

Randomization

The 120 households will be randomized in blocks of size 8 to one of the four treatment arms. In households randomized to treatment, all children aged 6-59 months of age will be treated, with the exception of one random child from within the household who will receive placebo. All children aged 6-59 months in households randomized to placebo will receive placebo. A random treated child from antibiotic arm households will be selected as the sentinel child for outcome assessment, and the untreated child from antibiotic arm households will also receive outcome assessment. Two children will be randomly selected from placebo households for outcome assessment.

Primary Outcome

We will compare diversity across arms at Day 9 and between time points. The primary outcome will be Simpson's index of alpha diversity. We will compare the mean Simpson's index between treatment arms with a t-test. All *P*-values will be calculated via permutation test.

Secondary Outcomes

As a secondary outcome, we will compare Shannon's index (L1 norm) between time points using a t-test. To compare if treatment significantly explains difference between the four treatment groups, we will compare Simpson's index (L1-norm) and Shannon's index (L2-norm) distances using PERMANOVA on bacterial reads.

To determine if there are differences in nutritional outcomes across treatment arms one month following treatment, we will calculate weight-for-height (WHZ), weight-for-age (WAZ), and height-for-age (HAZ) Z-scores based on 2006 WHO standards. We will compare mean WHZ, WAZ, HAZ, and mid-upper-arm circumference (MUAC) across treatment arms as continuous variables adjusting for baseline anthropometric values using an ANCOVA. We will also compare

the prevalence of stunting (HAZ <-2 SD) and moderate (WHZ <-2 SD) and severe (WHZ <-3 SD) acute malnutrition across study arms with a logistic regression model.

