3.2 Study Two: Antibiotic treatment and microbiome changes in children

Study Two is a randomized trial of a short course of antibiotics (azithromycin, co-trimoxazole, or amoxicillin) compared to no treatment. We will assess the effect of a short antibiotic course on intestinal and nasopharyngeal bacterial diversity and will test for antibiotic resistance in the resistome. Households with at least 2 children aged 6-59 months will be randomized in a 1:1:1:1 fashion to one of four study arms: 1) azithromycin, 2) amoxicillin, 3) co-trimoxazole, or 4) no treatment. All children minus one in the household will be treated, and we will assess the indirect effect of antibiotic treatment on the untreated child residing in the household. We will measure changes in microbiome three days following completion of the antibiotic course (primary outcome). During the final sample collection we will also complete a brief survey about the children's health particularly about diarrhea and respiratory infections. Finally, 4 weeks after the completion of the treatment we will evaluate the children's growth by doing anthropometric measurements.

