3.2.1 Sample Size

We will enroll 120 households into the four study arms (30/arm).

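### The primary comparison of Simpson's index between arms makes no stated use of the baseline swab; a baseline ANCOVA would be more precise unless the Day 0 to Day 9 correlation is very low

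*SAP*

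**What the plan says.** In the SAP, the Study Overview states: "Rectal and nasopharyngeal swabs will be collected pre-treatment (baseline) and on Day 9 following the 5 days of treatment". The schedule in Protocol 3.2.7 agrees, with swabs on Day 0 and Day 9.

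The SAP's Primary Outcome section opens: "We will compare diversity across arms at Day 9 and between time points". It then names Simpson's index as the primary outcome and compares the mean "index between treatment arms with a t-test", with all P-values by permutation. No covariate is named. Protocol 3.2 describes the primary outcome as change in the microbiome three days after the course ends. The protocol has no analysis section that says how baseline enters.

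For the continuous anthropometric outcomes under Secondary Outcomes, the SAP does specify "adjusting for baseline anthropometric values using an ANCOVA".

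Protocol 3.2.1 sets 120 households, 30 per arm. Neither document gives an alpha, a power, an SD, an expected difference or a correlation between the two swabs.

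**The concern.** Each assessed child should supply a pre-treatment value of the primary endpoint, yet the plan does not say how that value enters the arm comparison. Two readings fit the text.

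- **Day 9 values alone.** This discards the baseline.
- **Change from baseline.** This uses the baseline with a fixed coefficient of 1, and is less precise than Day 9 alone when r is below 0.5.

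The two readings can give different answers from the same data, and the choice is not fixed in advance. ANCOVA estimates the coefficient instead of fixing it at 0 or 1, so apart from a small estimation cost it is at least as precise as either. The SAP uses it for secondary outcomes and gives no reason for omitting it from the primary one. With 30 households per arm and no power calculation, precision that costs no extra data is worth having.

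**Working it through.** There is no stated power or sample-size calculation to reproduce, so the comparison is between methods.

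**Inputs.** 30 households per arm (Protocol 3.2.1). Assumed: two-sided alpha 0.05, one child per household, no dropout, common SD of 1, the same r in both arms. Since r is not given, a range is shown.

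**Formula.** Power is P(|T| > t(0.975, df)), where T is noncentral t with noncentrality d / √(v × 2/30) and v is the error variance relative to Day 9 alone.

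- Day 9 t-test: v = 1, df = 58. Here √(2/30) = 0.258, and 80% power is reached at d = 0.736.
- Change score: v = 2(1 − r), df = 58.
- ANCOVA: v = 1 − r², df = 57.

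The detectable difference is therefore close to 0.736 × √v. At r = 0.5, ANCOVA gives 0.736 × √0.75 = 0.637. At r = 0.3, the change score gives 0.736 × √1.4 = 0.870.

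| | r = 0.3 | r = 0.5 | r = 0.7 |
|---|---|---|---|
| Detectable difference, Day 9 t-test (SD) | 0.736 | 0.736 | 0.736 |
| Detectable difference, change score (SD) | 0.870 | 0.736 | 0.570 |
| Detectable difference, ANCOVA (SD) | 0.702 | 0.637 | 0.525 |
| Power at 0.6 SD, Day 9 t-test | 63% | 63% | 63% |
| Power at 0.6 SD, change score | 49% | 63% | 84% |
| Power at 0.6 SD, ANCOVA | 67% | 75% | 89% |
| Households needed relative to ANCOVA, Day 9 t-test: 1/(1 − r²) | 1.10 | 1.33 | 1.96 |
| Households needed relative to ANCOVA, change score: 2(1 − r)/(1 − r²) | 1.54 | 1.33 | 1.18 |

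**Small-sample cost of ANCOVA.** Chance baseline imbalance multiplies its variance by about 1 + 1/56 = 1.018. The detectable differences become 0.708, 0.643 and 0.530 SD, and power at 0.6 SD becomes 66%, 74% and 89%. At r = 0.1 ANCOVA gives 0.739 SD, and at r = 0 it gives 0.742 SD (0.742/0.736 = 1.008). Break-even is where (1 − r²) × 1.018 = 1, that is |r| of about 0.13.

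**Permutation P-values.** In simulation (blocks of 8, labels permuted within block, 3,000 runs of 499 permutations), ANCOVA had type I error of 5.1% with normal data and 4.8% with skewed data. Power at 0.6 SD was 65%, 73% and 89%, against 61–63% for the t-test.

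**Two placebo children.** The SAP says: "Two children will be randomly selected from placebo households for outcome assessment". If both are averaged within household, v for the unadjusted test is (1 + (1 + ICC)/2)/2. The detectable difference is then 0.64 SD (household ICC 0) to 0.74 SD (ICC 1), and with ANCOVA at r = 0.5 it is 0.55 to 0.64 SD. The relative gain is the same.

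**The case against.** The strongest reply is that nothing here is wrong: under randomisation the unadjusted t-test with permutation P-values is unbiased and keeps its type I error. That stands; the point concerns efficiency and an unspecified analysis.

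The second reply is that the gain depends on an unknown r, which antibiotics may weaken in treated children three days after the course. That limits the size. With equal arms and SDs, a common-slope ANCOVA behaves as if r were the average of the two arms. With r = 0.5 in controls and 0.1 in treated children the average is 0.3, giving 0.708 SD and 66% power at 0.6 SD rather than 74%. With 0.3 and 0.1 the average is 0.2, giving 0.727 SD against 0.736, about one point of power. Small gains remain in both cases.

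Third, ANCOVA needs a usable baseline, and Protocol 4.1 accepts that some nasopharyngeal swabs will fail. If 10% of baselines were missing (an assumption) and those children were dropped, ANCOVA at r = 0.3 would reach 0.749 SD, worse than the t-test. With mean imputation of the missing baselines it reaches 0.712 SD, so this calls for a stated rule rather than for abandoning the adjustment.

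Fourth, Day 9 values are the more natural reading of the arm comparison, and one sentence could settle that without ANCOVA. That is fair, but the sentence would leave the precision unused.

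Finally, with no expected effect or SD in the documents, nobody can say whether 0.74 SD is inadequate for this trial. That also stands.

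**Conclusion.** The point holds as a recommended change, not as a validity error. The planned arm comparison has no baseline term although the baseline is scheduled for collection, and the text does not settle whether Day 9 values or change scores are tested.

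Under the assumptions above, ANCOVA lowers the detectable difference from 0.74 SD to 0.70, 0.64 or 0.53 SD at r = 0.3, 0.5 or 0.7; the small-sample cost adds less than 0.01 SD to each. The payoff is lopsided: a loss under 1% if r is 0, against a Day 9 t-test needing about a third more households at r = 0.5. The reading of the text is secure. The size of the gain cannot be fixed from the documents, and it shrinks if treatment weakens r.

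**What to change.** In the SAP's Primary Outcome section, specify an ANCOVA of Day 9 Simpson's index on arm and the child's own baseline Simpson's index at the same body site. Add these points:

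- **P-value.** Keep the permutation test, permuting household assignments under the allocation scheme actually used. The SAP says "The 120 households will be randomized in blocks of size 8 to one of the four treatment arms", while Protocol 3.2.3 says the list is generated without blocking; reconcile these first.
- **Placebo households.** State whether one or both assessed children enter. If both, permute whole households.
- **Missing baselines.** Give a rule, such as mean imputation of the baseline, so that children with a Day 9 value are not dropped.
- **Change between time points.** If a within-arm change is wanted, list it separately as descriptive, because it is a different estimand.
- **Completeness.** The same sentence can name the body site, the three antibiotic-versus-control contrasts of Objective 2A and the alpha.

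The cost is SAP wording and one degree of freedom; both swabs are already scheduled. Multiplicity across the three contrasts is a separate decision. If a max-|t| adjustment were added (critical value about 2.38), power at 0.6 SD would be 48% without baseline and 52%, 62% and 81% with ANCOVA at r = 0.3, 0.5 and 0.7, so the adjustment should not be expected to pay for it unless r exceeds about 0.51.
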